### **Randomization and Blinding**

Not relevant: Single arm non-randomized study. No blinding.

### **Full analysis set (FAS)**

The full analysis set (FAS) includes all subjects who were enrolled and underwent at least one treatment with the study device.

Study synopsis.

### **Per-Protocol (PP)**

The per-protocol analysis set (PP) will consist of only patients who received the full treatment session and have photos from the 3-month follow up visit.

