### Study Synopsis

Protocol #	CLN 0827
Study Title	Evaluation of the Efficacy and Safety of a thermal fractional skin treatment system (Tixel®) for the treatment of facial and/or scalp actinic keratoses
Study Device	Tixel C (by Novoxel)
Device Description	Tixel technology is a thermal fractional skin treatment system powered by Thermo-Mechanical Action technology. Tixel employs a hot titanium tip which transfers direct heat to the skin. The proprietary tip is constructed of biocompatible temperature resistant titanium alloy cover mounted on gold plated copper base. The tip consists of an array of tiny pyramids which are heated to a temperature of 400°C. The apex of the pyramids transfers thermal energy to skin by very brief controlled contact time.
Study Design and Duration	
Single-center, Prospective, Open Label, with Before-After Study Design.
 
Up to 25 subjects will be enrolled to the study to provide at least 20 evaluable subjects. Subjects will be examined to determine the severity and extent of actinic keratoses.
 
All subjects will undergo 1-3 treatments (determined by the investigator assessment), 3-4 weeks apart.
 
Follow-up visits will be performed after the last treatment visit: 4 weeks (±7 days) and 12 weeks (±7 days).
 
The inclusion criteria would be mild to moderate thickness confluent actinic keratoses located to scalp and/or face.
 
Each subject will participate in the study for up to 20 weeks.
 
Total study duration is estimated to be up to 12 months from enrollment of the first subject until last subject visit (including FUs).

Investigational Treatment	This is a non-invasive thermo-mechanical treatment to the scalp and/or face using the Tixel technology. The handpiece will be pressed gently onto the scalp/facial skin while transferring heat in a predetermined setting.
Objectives	
Primary objective
 
To evaluate the efficacy of the Tixel technology (device) for the treatment of facial and/or scalp actinic keratoses.
 
Secondary objectives
 
 
• To evaluate procedure-related adverse reactions.
 
• To evaluate Subject's subjective downtime assessment.
 
• To Evaluate the pain of the treatment.
 
• To Evaluate the subject's satisfaction.
 

Study synopsis.

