	
13. Prior treatment with ablative laser, any laser or photo-dynamic therapy 3 months prior to enrollment.
 
14. Any cryotherapy or electrodesiccation 6 weeks prior to enrollment.
 
15. Systemic retinoid therapy within 6 months prior to enrollment, topical treatment with 5-Fluorouracil cream and/or imiquimod cream and/or diclofenac gel 6 months prior to enrollment.
 
16. Prior treatment with Tixel.
 
Treatment or treatment area related:
 
17. Face cannot be treated due to dermal disorder other than AKs, such as infection, surgical treatment etc.
 
Medical Conditions
 
18. Subject has a systemic disease manifested by AKs (e.g. immune suppression).
 
19. Significant systemic illness.

Study Evaluations
	
Efficacy:
 
Lesion count by the investigator, confirmed and documented using Standardized high-resolution digital photography of the treatment area (before and after marking the present actinic keratoses using a washable eyeliner) will be performed for each subject at baseline (before), at each treatment visit (prior to the treatment session) and at 4 and 12 weeks FU visits.
 
Safety:
 
 
• Skin safety throughout the study as determined by the investigator on site before and after treatments as well as by examining the post-treatment occurrences of complications and adverse events.
 
• Procedure related pain by VAS of 0-10 where a higher score indicates greater pain.
 

Primary Efficacy Endpoint:
	
The overall mean percentage reduction in actinic keratoses lesion count performed by the investigator manually, confirmed and documented using photograph images taken at baseline and at 12 weeks follow-up visit (or 12-weeks post last treatment if less than 3 treatments were done) (before and after marking the present actinic keratoses using a washable eyeliner) calculated as the relative change from baseline at 12 weeks. New lesions which were not existed in baseline will not be counted.

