## Study synopsis.

	
weeks follow-up visit. New lesions which were not existed in baseline will not be counted.
 

• Percentage of subjects that demonstrate a 26-50% in reduction in actinic keratoses lesion count 3 months after the final treatment.

• Percentage of subjects that demonstrate a 51-75% in reduction in actinic keratoses lesion count 3 months after the final treatment.

• Percentage of subjects that demonstrate more than 76% in reduction in actinic keratoses lesion count 3 months after the final treatment.

• Subjects' satisfaction assessed at the final follow-up visit (based on the subject experience questionnaire which includes 3 questions relating to treatment results, treatment experience and treatment expectations) graded on a score of 1- 5; 1 being not satisfied and 5 being very satisfied).

Safety Endpoints	

• Procedure related AEs

• Subject subjective downtime assessment - defined as the period of time following the procedure during which the subject felt unable/unwilling to go out in public due to skin reactions. The assessment will be recorded by the subject using the Subject Subjective Downtime Assessment following each treatment and will be collected at the site at the follow-up visits up to 4weeks FU following treatment 3 (third treatment).

• Procedure related pain by the subjects using VAS for pain of 0-10 where a higher score indicates greater pain.

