### **Study Hypothesis**

In this study we will test the following hypothesis:

- Mean reduction in AKs lesion count 3 months after the final treatment will be at least 50%.

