### **Statistical Analysis of Analysis Sets**

The FAS analysis set will serve as the main set for safety assessments. The primary efficacy assessment will be performed on the PP analysis set and as supportive analysis, on the FAS.

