## **Efficacy Analysis**

### ***Primary endpoint***

The overall mean percentage reduction in AK lesion count performed by the investigator manually, confirmed and documented using photograph images taken at baseline and at 12 weeks follow-up visit calculated as the relative change from baseline at 12 weeks will be calculated along with 95% confidence interval.

The Paired T-test or Signed rank test for two means (paired observations) (as is appropriate) will be applied for testing the statistical significance of the percentage reduction in in actinic keratosis lesion count from baseline at week 12 (compared to 50%).

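### The primary efficacy set turns on an undefined treatment-completion condition, so a single-arm mean judged against 50% is filtered on what happened after baseline

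*Combined protocol and SAP*

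**What the plan says.** The section Statistical Analysis of Analysis Sets states: "The primary efficacy assessment will be performed on the PP analysis set and as supportive analysis, on the FAS". Under Per-Protocol (PP), that set "will consist of only patients who received the full treatment session and have photos from the 3-month follow up visit". The FAS "includes all subjects who were enrolled and underwent at least one treatment with the study device".

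The amount of treatment is not fixed. Under Study Design and Duration the synopsis says: "All subjects will undergo 1-3 treatments (determined by the investigator assessment), 3-4 weeks apart". Its Primary Efficacy Endpoint row times the assessment at the 12-week visit, "or 12-weeks post last treatment if less than 3 treatments were done". The Study Endpoints section of the analysis plan restates that endpoint without this clause. The synopsis Safety Endpoints row has downtime forms collected "up to 4weeks FU following treatment 3 (third treatment"), as if a third treatment were the norm.

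The hypothesis is: "Mean reduction in AKs lesion count 3 months after the final treatment will be at least 50"%. Randomization and Blinding confirms a single arm with no blinding. Handling of Missing Data rules out imputation.

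**The concern.** The entry condition for the primary set refers to a complete amount of treatment that no section defines. Three readings are possible:

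- **One completed session.** This excludes hardly anyone.
- **All sessions the investigator chose.** This excludes subjects who did not finish their assigned course.
- **Three sessions.** This excludes everyone who had one or two, for whatever reason.

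Under the second and third readings, membership depends on events after baseline. The same unblinded investigator counts lesions before each treatment and decides how many treatments to give. The documents contain no rule for setting the intended number and no requirement to record it, so whether a subject completed the course could have to be judged in retrospect.

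With no control arm, the primary result is one mean set against a fixed value, so any selection of subjects goes straight into it. Removing subjects who stopped for pain or skin reaction would tend to raise the mean if they responded less well. Under the three-session reading, removing subjects who stopped because they had cleared would lower it.

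**Working it through.** **The plan's own figure.** Sample Size Estimation gives n = 20, SD 20 and a 95% z half-width of 8, so that 58% has a lower bound of 50%. Recomputed: 1.96 × 20/√20 = 8.77, and 58 − 8.77 = 49.2. The stated half-width does not reproduce. That is a separate matter, but it means there is no margin at the expected mean to absorb a change in the analysis set.

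**Inputs from the documents.** SD 20 percentage points, 20 evaluable subjects, benchmark 50%, two-sided 95% interval.

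**Assumptions.** The documents give no distribution of session numbers. Let k of the 20 subjects be removed, and let d be their mean reduction minus that of the subjects kept. SD is taken as 20 in whichever set is analysed.

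**Formulas.** Mean of those kept = overall mean − (k/20) × d. Lower limit = mean − t(0.975, n−1) × 20/√n. The half-widths are:

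- n = 20: 2.093 × 4.472 = 9.36
- n = 18: 2.110 × 4.714 = 9.95
- n = 16: 2.131 × 5.000 = 10.66
- n = 14: 2.160 × 5.345 = 11.55

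| Overall mean | k | d | Lower limit, all 20 | Kept: n, mean | Lower limit, kept | Crosses 50? |
|---|---|---|---|---|---|---|
| 60 | 6 | 0 | 50.6 | 14, 60.0 | 48.5 | yes, downward |
| 60 | 6 | +10 | 50.6 | 14, 57.0 | 45.5 | yes, downward |
| 58 | 6 | −15 | 48.6 | 14, 62.5 | 51.0 | yes, upward |
| 58 | 4 | −15 | 48.6 | 16, 61.0 | 50.3 | yes, upward |
| 58 | 2 | −15 | 48.6 | 18, 59.5 | 49.6 | no |
| 62 | 6 | 0 | 52.6 | 14, 62.0 | 50.5 | no |

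Three remarks on the table:

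1. The first row changes through smaller n alone. Rows two to four also involve selection.
2. In the third row, applying SD 20 within each subgroup gives a pooled SD of √[(18 × 400 + (6 × 14/20) × 225)/19] = 20.7. The limit for all 20 becomes 58 − 2.093 × 20.7/4.472 = 48.3, which is the same conclusion.
3. The arithmetic does not depend on why subjects were removed. Under the three-session reading, k is everyone with one or two sessions. Under the investigator's-course reading, k is only those who did not finish the assigned course. They are a subset of the first group, because the course never exceeds three.

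**The case against.** The strongest reply is that the text weighs against the damaging reading. The synopsis endpoint expressly provides for subjects with fewer than three treatments, the per-protocol definition states no number, and its wording is singular. A subject stopped because the lesions had cleared has had the chosen course and stays in. Only those who failed to complete it leave, which is ordinary per-protocol practice. The downtime wording that mentions a third treatment concerns form collection, not set membership.

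There are also safeguards. The FAS analysis is required as supportive, and without imputation it comes close to the analysis proposed here. Disposition of Subjects requires a list of deviations and of excluded subjects.

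The illustrations depend on assumed inputs, and some are fragile. Take 22 subjects, with six early clearers averaging 80% and sixteen others averaging 52%. With a within-group SD of 15.6, the limits are 50.8 for all and 43.7 for the sixteen. With SD 20, the limit for all is 49.3 and neither set passes.

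Most of this stands. It makes the investigator's-course reading the more plausible one, and it shows that a change of conclusion is not assured. It does not supply the missing definition, and it does not remove the dependence on post-baseline completion. Nor does it let the FAS decide the primary result.

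**Conclusion.** The point holds as a defect in how the primary analysis set is specified. The set depends on an undefined treatment amount. Even on the most plausible reading, it removes subjects according to unblinded, post-baseline completion, with no recorded intention to check against.

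The effect on the conclusion is conditional. With SD 20 and 20 subjects, removing four to six can move the lower limit across 50 when the overall mean is near the planned 58–60%. Removing two subjects who are 15 points worse at a mean of 58% does not, and nor does removing six at a mean of 62% with no difference. The session distribution and the group differences are assumptions throughout.

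A reader might infer three stronger things, none of which the documents support:

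- **That the set is limited to three-session subjects.** The synopsis endpoint points the other way.
- **That the result will reverse between readings.** The table includes cases where it does not.
- **That the plan provides for choosing the set once the counts are known.** It merely fails to prevent this, and the required listing of excluded subjects would make such a choice visible.

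**What to change.** Make the primary efficacy analysis the FAS subjects (at least one treatment) who have a photo-documented lesion count 12 weeks after their last treatment, whatever the number of sessions. This keeps the photographic condition and agrees with the synopsis endpoint.

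Keep the per-protocol set as supportive. Define its membership consistently with the one-to-three regimen and the fewer-than-three clause, and fix it before week-12 counts are reviewed. If it is defined as completion of the assigned course, the assigned number must be recorded for each subject.

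Reconcile the regimen, the two statements of the primary endpoint, the downtime wording and the per-protocol definition. How many treatments a subject should have is for the sponsor to settle. Show the primary result by number of sessions, descriptively only.

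The cost is mainly wording, plus one recorded item per subject if the assigned-course definition is used. The statistical downside is that subjects who stopped early for intolerance stay in the mean, which may be slightly less favourable.

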### **Statistical Analysis of Analysis Sets**

The FAS analysis set will serve as the main set for safety assessments. The primary efficacy assessment will be performed on the PP analysis set and as supportive analysis, on the FAS.

## **Statistical Analysis**

### **General Considerations**

Baseline demographic and other baseline characteristics, together with safety analyses will be performed on all enrolled subjects. Baseline values are defined as the last valid value prior to first treatment.

Statistical analyses of safety and secondary efficacy will be mainly descriptive in nature. Continuous variables will be summarized by a mean, standard deviation, minimum, 25th percentile median 75th percentile and maximum. Categorical variables by a count and percentage. Where confidence limits are appropriate, a two-sided 95% confidence interval will be constructed.

The required significance level of findings will be 5%. If statistical tests are performed, they will be two-sided and nominal *p*-values will be presented.

For comparison of means (continuous variables), the paired t-test or the Wilcoxon rank sum test will be used as appropriate. For comparison of proportions (categorical variables), the Chi-squared test or Fisher's exact test will be used as appropriate.

Analyses will be carried out using IBM Corp. Released 2017. IBM SPSS Statistics for Windows, Version 25.0. Armonk, NY: IBM Corp.

### **Demographic and Other Baseline Variables**

Demographic and baseline condition related characteristics will be tabulated. Continuous variables will be summarized by a mean, standard deviation, minimum, 25th percentile, median, 75th percentile and maximum, and categorical variables by a count and percentage.

### **Disposition of Subjects**

The number of subjects screened and reasons for screening failures will be presented.

The numbers of subjects who were enrolled will be provided, as well as the reasons for all enrollment discontinuations, grouped by major reason (e.g., lost to follow-up, adverse event, etc.). A list of discontinued subjects, protocol deviations, and subjects excluded from the analyses will be provided as well.

Study synopsis.

## **Efficacy Analysis**

### ***Primary endpoint***

The overall mean percentage reduction in AK lesion count performed by the investigator manually, confirmed and documented using photograph images taken at baseline and at 12 weeks follow-up visit calculated as the relative change from baseline at 12 weeks will be calculated along with 95% confidence interval.

The Paired T-test or Signed rank test for two means (paired observations) (as is appropriate) will be applied for testing the statistical significance of the percentage reduction in in actinic keratosis lesion count from baseline at week 12 (compared to 50%).

### ***Secondary endpoints***

- The mean change in in AK lesion count performed by the investigator manually, confirmed and documented using photograph images, from baseline at 4 and 12 weeks will be calculated along with 95% confidence interval.  
The Paired T-test or Signed rank test for two means (paired observations) (as is appropriate) will be applied for testing the statistical significance of the change in actinic keratosis lesion count from baseline at 4 and 12 weeks.
- The overall mean percentage reduction in AK lesion count performed by the investigator manually, confirmed and documented using photograph images taken at baseline and at 4 weeks follow-up visit calculated as the relative change from baseline at 4 weeks will be calculated along with 95% confidence interval.  
The Paired T-test or Signed rank test for two means (paired observations) (as is appropriate) will be applied for testing the statistical significance of the percentage reduction in in actinic keratosis lesion count from baseline at 4 weeks (compared to 50%).
- The percentage of subjects with lesion count reduction from baseline at 3 months between 26% and 50% will be calculated along with 95% exact confidence interval for proportions.
- The percentage of subjects with lesion count reduction from baseline at 3 months between 51% and 75% will be calculated along with 95% exact confidence interval for proportions.
- The percentage of subjects with lesion count reduction from baseline at 3 months higher than 76% will be calculated along with 95% exact confidence interval for proportions.
- The Subject satisfaction assessment score will be calculated along with 95% confidence interval.

Each of the above measures will be summarized by descriptive statistics by data type.

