### Study Endpoints

#### Primary efficacy endpoint

The overall mean percentage reduction in AK lesion count performed by the investigator manually, confirmed and documented using photograph images taken at baseline and at 12 weeks follow-up visit (before and after marking the present actinic keratoses using a washable eyeliner) calculated as the relative change from baseline at 12 weeks. New lesions which were not existed in baseline will not be counted.

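### The responder bands leave a gap between 75% and 76%, so a subject with a 76% reduction is counted in no band

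*Combined protocol and SAP*

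**What the plan says.** The bands are defined in three places in the combined protocol and SAP, and all three agree.

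- **Synopsis, Secondary Efficacy Endpoints**, and **Study Analysis Plan, Secondary efficacy endpoints**: after a 26-50% band come "Percentage of subjects that demonstrate a 51-75% in reduction in actinic keratoses lesion count 3 months after the final treatment" and "Percentage of subjects that demonstrate more than 76% in reduction in actinic keratoses lesion count 3 months after the final treatment".
- **Efficacy Analysis, Secondary endpoints**: "The percentage of subjects with lesion count reduction from baseline at 3 months between 26% and 50% will be calculated"; "The percentage of subjects with lesion count reduction from baseline at 3 months between 51% and 75% will be calculated"; and "The percentage of subjects with lesion count reduction from baseline at 3 months higher than 76% will be calculated". Each percentage is to be reported with an exact 95% confidence interval.

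The percentage reduction in the primary endpoint is "calculated as the relative change from baseline at 12 weeks". It is a ratio of lesion counts, so it need not be a whole number. No section says whether it is rounded before a subject is placed in a band. General Considerations describes the secondary efficacy analysis as mainly descriptive.

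**The concern.** The two lower bands meet in whole percents: one ends at 50 and the next begins at 51. The upper junction does not. The middle band ends at 75 and the top band begins strictly above 76. A subject who falls between them has responded well but appears in neither upper band.

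Each band is a named secondary endpoint with its own interval, so the omission would show directly in the efficacy table. Without a rounding rule, the analyst must also choose a convention, in an open-label single-arm study, and that choice moves some subjects into or out of the top band.

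**Working it through.** The plan states no figure that depends on the bands, so there is nothing to reproduce first. The check applies the limits as written to every attainable result.

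**Inputs.** Bands [26, 50], [51, 75] and >76 (Efficacy Analysis, Secondary endpoints); 20 evaluable subjects (Synopsis); mean 58% and SD 20 (Sample Size Estimation). The documents give no baseline lesion counts, so the ranges in step 4 are assumptions.

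**Formula.** With m baseline lesions and k cleared, the reduction is p = 100 × k/m.

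**Step 1: unrounded values.** The gap is 75 < p ≤ 76. The smallest baseline count that can reach it is 25. Up to 40 lesions there are four cases:

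- 19/25 = 76.00%
- 22/29 = 75.86%
- 25/33 = 75.76%
- 28/37 = 75.68%

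**Step 2: values rounded to the nearest whole percent.** The gap is every p that rounds to 76. The smallest baseline count is 17. Up to 40 lesions there are eight cases: the four above plus

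- 13/17 = 76.47%
- 16/21 = 76.19%
- 26/34 = 76.47%
- 29/38 = 76.32%

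These four are in the top band unrounded and in no band rounded. Exactly 76% is in no band either way. The two conventions are alternatives, so their losses do not add.

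**Step 3: effect of one subject.** 1/20 = 5 percentage points. For example, 8/20 = 40% (exact 95% CI 19.1% to 63.9%) against 9/20 = 45% (23.1% to 68.5%).

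**Step 4: how often (illustration only).** Take reductions as Normal(58, 20), assign the probability to the nearest attainable k/m, and average over a uniform range of m. A gap case k/m has probability Φ((100(k+½)/m − 58)/20) − Φ((100(k−½)/m − 58)/20).

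- Unrounded, the four cases have probabilities 0.0532, 0.0461, 0.0407 and 0.0365, which sum to 0.1766 (before rounding of the terms).
- Rounded, the eight cases sum to 0.3887, of which 13/17 contributes 0.0766 and 16/21 contributes 0.0628.

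| Convention | Baseline range | Per subject | Expected of 20 |
|---|---|---|---|
| Unrounded | 5-24 | 0 | 0 |
| Unrounded | 5-40 | 0.1766/36 = 0.49% | 0.10 |
| Unrounded | 20-40 | 0.1766/21 = 0.84% | 0.17 |
| Rounded | 5-16 | 0 | 0 |
| Rounded | 5-24 | (0.0766 + 0.0628)/20 = 0.70% | 0.14 |
| Rounded | 5-40 | 0.3887/36 = 1.08% | 0.22 |
| Rounded | 20-40 | (0.3887 − 0.0766)/21 = 1.49% | 0.30 |

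**Step 5: the lower junction.** Unrounded values between 50% and 51% also have no band, but this needs at least 51 baseline lesions (26/51 = 50.98%). Whole-percent rounding closes that gap and leaves the one at 76%.

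**The case against.** The case against giving this weight is strong.

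- **Rarity.** Even in the least favourable range shown, fewer than one subject is expected in the gap across three trials of 20. With low baseline counts it cannot occur.
- **No wrong number.** The percentage above 76% would be computed correctly as worded. The 5 points are a difference from a definition that the plan does not use, and they arise only if a subject lands in the gap.
- **Bands not exhaustive.** The plan never says that the bands cover everyone, and it has none below 26%. Under its own mean and SD, Φ((25 − 58)/20) = Φ(−1.65), about 5% or one subject of 20, would be at or below 25%. That is more than the gap would take.
- **Nothing rests on it.** The bands are not tested, and the hypothesis, sample size and primary test do not use them.

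All of this stands as a limit on severity. It does not remove the defect. Leaving out poor responders is a coherent reporting choice. A hole between two adjacent responder bands has no stated reason and looks like a slip for 76% or more. Neither unrounded values nor rounding to the nearest whole percent closes it.

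**Conclusion.** The concern holds and is minor. Followed exactly, the plan leaves reductions above 75% and up to 76% (unrounded), or those rounding to 76% (whole percents), outside every band. This follows from the wording alone and needs no assumption.

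Its frequency is unknown, because baseline counts are not given. It is nil if every subject has 24 or fewer lesions (unrounded) or 16 or fewer (rounded). The illustrated 0 to 0.30 subjects of 20 rests on assumed uniform baseline ranges and on the plan's 58% and SD 20.

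A subject in the gap still counts in the primary mean percentage reduction and in the mean change in lesion count. The trial's main conclusion is not at risk.

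**What to change.** Make the bands contiguous and use the same wording in the synopsis, the endpoint list and the analysis section. Either of these works:

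1. On unrounded values: >25% to ≤50%, >50% to ≤75%, and >75%.
2. With rounding to the nearest whole percent stated: 26-50%, 51-75%, and ≥76%.

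Checked over all k/m for m from 1 to 200, each option puts every value above its lowest limit in exactly one band. They classify every subject identically for baseline counts up to 50. They first differ at 13/51 = 25.49% (lowest limit) and 40/53 = 75.47% (top limit), so the choice is the sponsor's.

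Two cautions apply. Changing only the top band to at least 76%, without a rounding rule, is not enough, because 22/29 = 75.86% would still be in no band. Both options also settle the lowest limit: 7/27 = 25.93% is below the first band if the present text is read unrounded, and would enter it under either option. The change should say so.

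The cost is a wording amendment, best made before the 3-month counts are seen. It needs no new data and does not change the primary analysis or the sample size.
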